9.0 TREATMENT/INTERVENTION PLAN

9.1 Skin Cream Application

Arm 1 consists of patients randomized to standard of care arm (Eucerin) and Arm 2 is the experimental arm (MF 0.1%). Patients will start applying the agent to the chest wall twice daily beginning on the first day of radiation treatment and continuing 10-14 days post-completion of RT.

Patient education regarding amount to be applied (amount depending on body habitus) and area of treatment field will be reinforced by the R.N. prior to the first radiation treatment. Patients will be instructed to apply cream to the upper outer quadrant, upper inner quadrant, lower outer quadrant, and lower inner quadrant, as well as irradiated nodal fields. They will be instructed to apply cream in a thin, uniform layer twice a day, in the morning and evening, and not within the immediate 4 hours prior to radiation treatment. Patients will be informed that application immediately following radiation treatment is acceptable for those scheduled to receive morning treatments.

Patients will be instructed to wash the area daily using a mild soap such as Dove or Cetaphil, and to pat skin dry prior to cream application. Patients will be instructed to avoid the use of any exfoliating agents, such as loofah, sponges, or scrubs. Skin will not be washed for at least 8 hours after each application.

Patients will be instructed to wear soft, loose clothing to cover the treated areas, but not to use any occlusive dressings, and to avoid exposure to the sun. The use of sunscreens should be discouraged, with a preference to using clothing to cover the treatment area when exposure to the sun is expected. Patients will be discouraged from scratching the treated area and using possible skin irritants such as aftershaves, colognes, and perfumes. Aluminum-free deodorants will be permitted. Topical and/or systemic treatments for prophylaxis of dermatitis other than assigned cream will be prohibited during the study.

The topical agents will be blinded and dispensed after randomization at patient's simulation visit or at the radiation setup in 130 gram jars labelled with patient's name and MRN by the Memorial Sloan-Kettering Cancer Center (MSKCC) pharmacy. It is estimated that the average patient will require approximately 3 grams of cream per application, and will require one additional prescription for a jar of study cream during the 7 week trial. During weekly assessment of compliance at routine status check, date of dispensation of second jar will be recorded on provider assessment sheet as an additional indicator of compliance.

Patients will return to clinic for a follow up visit at 10-14 days following the completion of RT. At this visit the study investigator will perform a skin assessment and the patient will complete the Skindex-16.

9.2 Chest Wall Radiotherapy

The radiation treatment included in this study represents the institutional standard of care and is not influenced by the patient's decision to participate in this study. Either photons or electrons will be used for the primary radiotherapy treatment, depending on reconstruction status of the patient. Patients without reconstruction receive electrons directed en face to

the chest wall with customized bolus, or photon tangents with daily bolus over the chest wall. Patients who have a reconstruction are treated with two tangential photon beams and bolus over the reconstructed breast everyday. Treatment breaks necessitated by severe toxicities will be recorded and will not be considered deviations.

Concurrent delivery of chemotherapy will not be allowed. Biologic agents and hormonal therapy during radiation will be permitted.

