1.0 PROTOCOL SUMMARY AND/OR SCHEMA

This is a double-blinded, randomized trial. Its purpose is to compare the steroid cream mometasone furoate 0.1% (MF), with standard emollient skin care, Eucerin, on the prevention of grade 2 or higher skin toxicities in breast cancer patients receiving PMRT to the chest wall and regional lymph nodes. Patients will be stratified based on two variables: the presence of a reconstruction in order to achieve a balanced population of patients being treated with either photon or electron beams, and body mass index (BMI <30 vs ≥30).

Female breast cancer patients who have received mastectomy + axillary surgery and will undergo postmastectomy radiation (PMRT) at our institution are eligible for this study. Enrollment of 143 patients is expected to take place over 3 years.

Skin toxicities using the Common Terminology Criteria for Adverse Events (CTCAE) v.4 scale will be scored by evaluating RN or MD . Assessments will be completed at baseline, weekly during radiation therapy (RT), and 10-14 days following the completion of RT. Patient-reported skin symptoms will also be assessed at baseline, at week 5 of RT, and 10-14 days following completion of RT.

Screening	Randomization	Pre-RT	Weekly During RT (5 weeks, 50 Gy)	Follow-up (10-14 Days Post-RT)
143 breast cancer patients status post mastectomy + axillary surgery, ± chemotherapy 
 Stratifications: 
 Reconstruction Yes vs no Body Mass Index <30 vs ≥30 	Eucerin BID 
 or mometasone furoate 0.1% BID 	
 Baseline H and P Baseline Provider Skin Toxicity Assessment Baseline Skindex-16 questionnaire Patient education on topical cream usage 	
 Weekly status checks Weekly skin cream compliance assessed Provider Skin Toxicity Assessment Skindex-16 questionnaire during Week 5 of RT 	
 Skin cream compliance assessed Provider Skin Toxicity Assessment Skindex-16 questionnaire

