8.0 PRETREATMENT EVALUATION

The History and physical exam in Radiation Oncology will include information on race/ethnicity, age, body mass index, chemotherapy status, hormone therapy, smoking history/status, diabetes, high blood pressure, Eastern Cooperative Oncology Group (ECOG) performance, and reconstruction status.

Radiation Treatment Planning will be approved by the treating MD, in order to determine type of chest wall radiotherapy (photons vs electrons) to be administered, as outlined in section 9.1.

Baseline Provider Skin Toxicity Assessment will be done within 14 days prior to the start of RT.

Patients will complete a baseline Skindex-16 Questionnaire and Fitzpatrick Skin Classification within 14 days prior to the start of RT (Appendix 1 and 2).

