14.0 BIOSTATISTICS

This is a double-blinded, randomized trial (see Section 15.2 for details of randomization) to compare MF 0.1% cream with standard skin care (Eucerin) on the prevention of moderate to severe skin toxicities in breast cancer patients receiving post-mastectomy radiation to the chest wall and regional lymph nodes. A patient is deemed to have developed skin toxicity if she has a grade ≥ 2 skin toxicity as defined in Section 3.4 within 7 weeks from the beginning of radiation.

Based on estimates provided by radiation oncologists at our institution, the rate of grade ≥ 2 toxicity using Eucerin as skin care for chest wall radiation is $\approx 50\%$. This estimate is slightly lower than the findings from the Spierer study cited in section 3.2, to reflect this study's inclusion of patients treated with photons (in the presence of reconstruction) as well as electrons. We expect that the usage of MF can reduce this rate to 25%. 124 evaluable patients are needed for the comparison, with 62 patients in each arm. Two-sample, two-sided proportion tests will be used to derive the statistical significance. One interim analysis will be conducted when 31 patients in each arm have been enrolled and evaluated using the O'Brien-Flemming procedure, which will declare significance if the test p-value is less than 0.005. Correspondingly the final analysis will declare significance if the test p-value is less than 0.048. This design has a power of approximately 0.83 (i.e., detecting the true toxicity rate of 25% or lower) at the type I error (i.e., declaring MF more effective while it yields the same toxicity rate as Eucerin) rate of 0.05 based on 100000 statistical simulations.

All deaths unrelated to the toxicities, and patients lost to follow-up (before toxicities can be evaluated), will be excluded from the comparison and new patients will be accrued for replacement. To this end we plan to enroll an additional 15% of patients. Therefore our final proposed accrual is about 143 patients, which is expected to be done in 3 years.

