15.2 Randomization

Randomization will be done at MSKCC. Patients will be randomized to the MF 0.1% cream arm or the standard skin care arm with Eucerin at the ratio of 1:1. For patients enrolled at MSKCC, after eligibility is established and immediately after consent is obtained, the RSA will register participants in the PPR system and randomize participants using the Clinical Research Database (CRDB), by calling the MSKCC PPR Office at [contact] between the hours of 8:30 am and 5:30 pm, Monday to Friday. Randomization will be accomplished by the method of random permuted block, and will be stratified by the presence of breast reconstruction and BMI. After treatment arm is determined by randomization, RSAs at MSKCC will notify the research staff of the participant ID via email within 24 hours of randomization. Since this is a double blind study, the research participants' treatment assignments can be viewed in the CRDB only by the hospital pharmacists who are dispensing the study drugs.

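### Stratifying on reconstruction does not guarantee photon/electron balance among unreconstructed patients, and the primary test adjusts for neither beam nor the strata

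*Combined protocol and SAP*

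**What the plan says.** Section 1.0 gives the purpose of the first stratification factor: "the presence of a reconstruction in order to achieve a balanced population of patients being treated with either photon or electron beams". Section 14 makes the same link when it explains why the control rate is set a little below that of a cited series: the rate is meant "to reflect this study's inclusion of patients treated with photons (in the presence of reconstruction) as well as electrons".

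Section 9.2 describes the beams differently. For one group the link is exact: "Patients who have a reconstruction are treated with two tangential photon beams and bolus over the reconstructed breast everyday". For the other it is not: "Patients without reconstruction receive electrons directed en face to" the chest wall, "or photon tangents with daily bolus over the chest wall".

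On allocation, Section 15.2 states: "Randomization will be accomplished by the method of random permuted block, and will be stratified by the presence of breast reconstruction and BMI". Beam is not a factor. Section 8.0 has the treating physician approve the plan "in order to determine type of chest wall radiotherapy (photons vs electrons) to be administered", so planned beam is on record before treatment starts.

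The primary analysis in Section 14 is a two-sided, two-sample test of proportions with no strata or covariates. The analysis of covariance and Cox models mentioned later in that section concern secondary endpoints, are optional, and do not name beam.

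**The concern.** The plan uses reconstruction as a stand-in for beam, but by its own account reconstruction fixes beam in only one of the two groups. All electron patients are unreconstructed, and that stratum also contains photon patients. Balance on beam, the stated reason for the factor, is therefore not secured where the beams actually mix.

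The plan itself regards beam as prognostic: it stratifies for it by proxy and lowers the control rate because of it. If beam turns out visibly uneven between arms, the pre-specified test takes no account of it, and any adjustment chosen afterwards would be post hoc and open to dispute. Part of the precision that stratified randomisation can offer is also left unused.

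**Working it through.** **1. The plan's own figure.** Inputs from Section 14: 62 per arm, 50% vs 25%, final threshold p < 0.048 (|z| > 1.977).

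- Null SE = √(2 × 0.375 × 0.625 / 62) = 0.0870
- Alternative SE = √((0.50 × 0.50 + 0.25 × 0.75) / 62) = 0.0840
- Power = Φ((0.25 − 1.977 × 0.0870) / 0.0840) = Φ(0.93) = 0.824

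A two-look simulation (400,000 runs, pooled z, no continuity correction) gives 0.835. The stated value of about 0.83 is reproduced.

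**2. Size of the chance imbalance.** The documents give neither the share unreconstructed (u) nor the share of those on electrons (e). Assume u = 30–70% and e = 25–75%. With reconstruction balanced, the SD of the between-arm difference in electron share is about √(2·u·e(1−e)/62):

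- Lowest case, u = 0.3, e = 0.25 (19 unreconstructed per arm): √(2 × 19 × 0.1875)/62 = 0.043
- Middle case, u = 0.5, e = 0.5 (31 per arm): √(2 × 31 × 0.25)/62 = 0.064
- Highest case, u = 0.7, e = 0.5 (43 per arm): √(2 × 43 × 0.25)/62 = 0.075

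In simulation, 95% of trials fall within about 8 points (lowest case) to 15 points (highest case). At the interim, with 31 per arm, the middle case becomes √(2 × 0.5 × 0.25/31) = 0.090.

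**3. Effect on the treatment difference.** Shift = imbalance × toxicity gap between beams. The gap is also undocumented.

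- Gap of 20 points: 0.081 × 20 = 1.6 to 0.145 × 20 = 2.9 points (95% limits)
- Gap of 30 points: 0.081 × 30 = 2.4 to 0.145 × 30 = 4.4 points

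The planned effect is 25 points and the standard error of the arm difference is about 8.4 points. That standard error already includes this source of variation.

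**4. Error rates with and without adjustment.** Final look only, p < 0.048, e = 0.5, mometasone halving the risk, 200,000 runs. The adjusted test is Cochran-Mantel-Haenszel (CMH) over reconstructed, unreconstructed-photon and unreconstructed-electron. The last column adds randomisation stratified on beam.

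| Control rate, photon / electron | u | Type I, unadjusted | Type I, CMH | Power, unadjusted | Power, CMH | Power, CMH + beam-stratified allocation |
|---|---|---|---|---|---|---|
| 45% / 60% | 0.5 | 0.052 | 0.048 | 0.816 | 0.810 | 0.818 |
| 45% / 60% | 0.7 | 0.052 | 0.047 | 0.838 | 0.831 | 0.837 |
| 40% / 70% | 0.5 | 0.050 | 0.048 | 0.801 | 0.806 | 0.814 |
| 40% / 70% | 0.7 | 0.052 | 0.048 | 0.841 | 0.846 | 0.854 |
| 40% / 80% | 0.5 | 0.048 | 0.047 | 0.836 | 0.850 | 0.859 |
| 40% / 80% | 0.7 | 0.049 | 0.048 | 0.883 | 0.897 | 0.904 |

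With a gap of only 3 points and half of patients unreconstructed, the CMH test loses about 1 point: 0.838 to 0.829 with 30% photons among the unreconstructed, and 0.829 to 0.819 with 50%.

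Across these scenarios, adjustment under the current randomisation changes power by about −1 to +1.5 points. Adding beam-stratified allocation changes it by −0.1 to +2.3 points relative to the current plan.

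The highest type I error in any scenario tried was 0.054 (40% / 60%, u = 0.5, overall rate 45%). That is discreteness, not beam. Summing Bin(x; 62, p) × Bin(y; 62, p) over all pairs with |z| > 1.977 gives 0.054 at p = 0.45 and 0.053 at p = 0.50, with no beam effect at all.

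These runs do not split by BMI. Adding it to a CMH test makes the cells smaller, so if BMI is also unrelated to toxicity the loss would be somewhat more than 1 point.

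**The case against.** The strongest reply is that nothing here threatens the trial's validity. Stratification does balance the all-photon reconstructed patients. Among the rest, 1:1 randomisation balances beam in expectation.

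A reader might infer that the physician's choice of beam could differ by arm. The documents do not support that. Section 9.2 says radiotherapy follows institutional standard and is unaffected by participation, Section 12.1 blinds the clinical team, and Section 15.2 limits sight of the assignment to the dispensing pharmacists. This part of the reply stands in full.

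The gap between beams may also be small. Section 14 puts the control rate at about 50%, against 52% in the cited series, to allow for photon patients. If half of patients are unreconstructed and 30–50% of those get photons, photon patients are 65–75% of the total, and a 2-point drop implies a gap of 2/0.75 = 2.7 to 2/0.65 = 3.1 points. The 52% is RTOG grade 3–4, a different endpoint, so this shows only what the plan assumed. It is still a fair reason not to rely on a 30-point gap.

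A reader might also conclude that randomisation must be re-stratified. The documents do not settle whether that is workable. Section 15.2 randomises immediately after consent, and the schedule table in Section 10.2 lists plan approval and randomisation under the same visit without an order. Six cells would average 143/6 ≈ 24 patients, and 62/6 ≈ 10 at the interim.

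What survives is narrower: the stated rationale does not match Section 9.2, and no pre-specified analysis covers the gap.

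**Conclusion.** The point holds as a modest gap in design rationale and analysis. Balance on beam is not guaranteed among unreconstructed patients, and the primary test uses neither beam nor the stratification factors.

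It does not support the stronger readings that the arms will be unbalanced on beam, that the comparison is biased, that type I error is inflated, or that adjustment reliably raises power. The sample size does not change. The effect on power is about −1 to +2 points, its sign depending on how strongly beam predicts toxicity.

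The contradiction between sections is in the text and needs no assumption. The sizes rest on assumed beam shares and beam-specific toxicity rates, and on final-look simulations. The case for acting is that pre-specification is nearly free and protects the main result from a dispute over a factor the plan itself treats as prognostic.

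**What to change.** 1. Keep the current randomisation.
2. In Section 14, pre-specify the primary comparison as a CMH or covariate-adjusted test using a three-level factor (reconstructed; unreconstructed, planned electrons; unreconstructed, planned photons) and the BMI stratum. Use the beam recorded at plan approval, not the beam delivered. Apply the same statistic at the interim and final looks, with the thresholds unchanged.
3. Keep the unadjusted test as a sensitivity analysis, and report planned beam by arm.
4. Reconcile the rationale in Sections 1.0 and 14 with Section 9.2, so that reconstruction is described as a partial proxy for beam. This concerns the statistical rationale only and implies no change to radiotherapy.
5. Optional: use the three-level factor in randomisation, but only if planned beam is known before allocation. Sections 10.2 and 15.2 would first need to state the order.

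Cost: a few sentences, one recorded variable and slightly more analysis work. Power may fall by about 1 point, or slightly more once BMI is included, if these factors barely predict toxicity.

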10.0 EVALUATION DURING TREATMENT/INTERVENTION

10.1 Evaluation During Radiation

Weekly status checks including assessment of patient compliance and Provider Skin Toxicity Assessments using CTCAE 4.0 during radiation treatment will be performed according to standard practice in the Department of Radiation Oncology. The patient will complete the Skindex-16 form during the last week of RT (week 5). The amount of topical agent used will be evaluated based on timing of patient's request for refill by an R.N. in order to assess compliance with the treatment regimen and will be documented on the Provider Skin Toxicity Assessment form.

10.2 Evaluations After Radiation

Follow-up visits will be completed 10-14 days after the completion of RT. At this time, provider assessment of skin toxicity will be performed by the physician and RN, and the patient will complete another Skindex-16 form.

Tests and Observations	Consultation	Simulation	Set-Up/ Treatment #1	During Treatment (5 weeks)	10-14 Days Following Completion of Treatment (CoT)
History and Physical	X			Weekly Status checks	
Radiation Treatment Plan approval		X			
Randomization		X			
Patient Teaching and Administration of Topical Agent		X	X	Assess compliance weekly	
Provider Assessment of Skin Toxicity		X		Provider assessment weekly	X
Patient Assessment of Fitzpatrick Category (Appendix 2)		X			
Patient Assessment of Skin Toxicity (Appendix 1)		X		Week 5 only	X

11.0 TOXICITIES/SIDE EFFECTS

The patient will be monitored for erythema and desquamation in the radiation field, which are expected side effects from chest wall radiotherapy. Some patients may develop moist desquamation, which usually heals within a few weeks and is treated with Silvadene cream and/or hydrocolloid dressings. Treatment breaks secondary to severe acute skin toxicities and/or cellulitis during radiation are not anticipated.

If a patient develops grade 2 or greater moist desquamation, or adverse reaction to the topical agent, she will be instructed to discontinue study cream and will receive standard of care management as determined by the patient's provider. These patients will continue to be evaluated according to study guidelines, and intervention will be noted on the Provider Skin Toxicity Assessment form. Patients who develop grade 2 erythema without the presence of moist desquamation will continue to use study cream without deviation from protocol guidelines.

Side effects from MF are uncommon. In controlled clinical studies of MF, the incidence of adverse reactions of burning, pruritus, and skin atrophy was 1.6%. Infrequent side effects include irritation, dryness, folliculitis, hypertrichosis, acneiform eruptions, hypopigmentation, allergic contact dermatitis, secondary infection, striae, and miliaria. Systemic absorption may produce reversible hypothalamic-pituitary-adrenal (HPA) axis suppression, manifestations of Cushing syndrome, hyperglycemia, and glycosuria.

Eucerin Original side effects are rare but include skin redness, irritation, and itching.

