3.2 Radiation-Induced Dermatitis

A variety of patient and treatment-related factors such as fractionation schedules, dose, size of the treatment field, concurrent chemotherapy, use of bolus or other beam-modifying devices, and individual genetic variation can affect the intensity of the skin reaction to radiation (Tucker, Turesson et al. 1992). The majority of data available regarding side effects are generated from patients receiving radiation to the intact breast, not the chest wall after mastectomy. Side effects are generally categorized as acute if occurring during or within 6 weeks of radiation treatment and late if occurring >6 weeks after completion of treatment. A common acute toxicity is dermatitis within the irradiated volume. Typically, the skin becomes erythematous and/or hyperpigmented, and may desquamate, in particular in the area of skin folds such as the axilla, supraclavicular fossa, or inframammary fold. Desquamation may be dry or moist. Progressive erythema may be seen after 10-20 Gy, depending on the fractionation schedule (Turesson and Notter 1975), and reaches maximal intensity approximately 1-2 weeks following the completion of treatment. An example of the development of moist desquamation and grade 2 erythema in a woman 1 week post-completion of PMRT to an unreconstructed chest wall is illustrated in Appendix 3.

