12.0 CRITERIA FOR THERAPEUTIC RESPONSE/OUTCOME ASSESSMENT

12.1 Assessment of Primary Objective

The grading of skin toxicity will be based on the CTCAE version 4.0 scale as defined in section 3.4. To ensure unbiased skin toxicity measurement, both the clinical team and patient will be blinded to the treatment assignment. The type of skin toxicity (moist desquamation or grade ≥ 2 erythema), maximal score, its location within the target (chest wall or axilla), and time to occurrence will be recorded weekly during RT and at week 2 follow-up on the Provider Skin Toxicity Assessment Form. Following the post-treatment visit, the patient will not need to return to the clinic for other follow-up visits unless otherwise specified by the treating physician.

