17.0 PROTECTION OF HUMAN SUBJECTS

The procedures involved in this study are felt to be of minimal risk, meaning that the probability and magnitude of harm or discomfort anticipated in the research are not greater in and of themselves than those ordinarily encountered in daily life or during the performance of routine physical or psychological examinations or tests. The benefit derived from the study would be prevention of moderate to severe skin toxicities in breast cancer patients undergoing chest wall radiation. Patients or their legal guardians will receive comprehensive explanation of the proposed treatment options being offered on this protocol, including the nature of the investigation, rationale, alternative treatments and any known previously observed side effects, the investigational nature of the study, and the potential benefits and risks of the intervention. Participation in this trial is voluntary. All patients will be required to sign a statement of informed consent, which must conform to IRB guidelines.

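### Reactions to the study creams are captured only in part, with no graded collection or by-arm summary, and planned observation ends when scheduled cream use ends

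*Combined protocol and SAP*

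**What the plan says.** Section 11 begins with what is expected from radiotherapy: "The patient will be monitored for erythema and desquamation in the radiation field". Two paragraphs later it turns to the creams. For MF it states that "the incidence of adverse reactions of burning, pruritus, and skin atrophy was 1.6" per cent, and adds: "Infrequent side effects include irritation, dryness, folliculitis, hypertrichosis, acneiform eruptions, hypopigmentation, allergic contact dermatitis, secondary infection, striae, and miliaria". It also names systemic steroid effects. For Eucerin it names redness, irritation and itching.

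Section 11 has a rule for cream reactions. A patient with a reaction to the cream, or with moist desquamation of grade 2 or more, is told to stop the cream. She stays under evaluation, and the intervention is noted on the provider form.

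Section 12.1 sets out the data for the primary objective. Besides when a reaction first appears, they are: "The type of skin toxicity (moist desquamation or grade ≥ 2 erythema), maximal score, its location within the target (chest wall or axilla"). The section says that all of these "will be recorded weekly during RT and at week 2 follow-up on the Provider Skin Toxicity Assessment Form". Once that last visit is done, "the patient will not need to return to the clinic for other follow-up visits unless otherwise specified by the treating physician".

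Sections 3.4 and 12.2 provide the Skindex-16 at baseline, in week 5 of radiotherapy (RT) and 10-14 days after RT. Section 17.2 requires serious adverse events (SAEs) to be reported with their relationship to treatment. Section 14 plans analyses of grade 2 or higher skin toxicity, Skindex-16 scores, maximum toxicity and time to toxicity.

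**The concern.** The protocol knows which local reactions MF can cause, but it describes no routine by which a provider looks for them, grades them and records them in both arms. If such data are not collected at the visits, they cannot be recovered at analysis.

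The trial compares about seven weeks of a twice-daily steroid cream with an emollient for prevention. A positive result would need to be weighed against infection, contact reactions and atrophy, and the plan would leave little comparative information for that.

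There is also a link to the endpoint. Section 11 gives irritation for both creams, contact dermatitis for MF and redness for Eucerin. A cream reaction could look like erythema, and no field is described that would let the analysts examine this.

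**Working it through.** **Plan's own figures.** The plan gives no precision for harms. The sample size behind the figures below does reproduce. With 62 per arm, 50% against 25%, the normal approximation gives power 0.828 at two-sided 0.05. A simulation of the two-look design (p < 0.005 at 31 per arm, then p < 0.048 at 62) gives 0.835, against a stated 0.83. Accrual is 124 × 1.15 = 142.6, or 143 as stated. The point does not depend on these.

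**What each route captures.**

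| Route | Captures | Leaves out |
|---|---|---|
| Stopping rule (Section 11) | Recognised cream reactions; the intervention | Type, grade and onset are not specified; the rule also covers moist desquamation, and no field separating the two reasons is described |
| Skindex-16 (Sections 3.4, 5.3, 12.2, 14) | Subjective symptoms at three time points, compared between arms | Averaged scores only; not a substitute for provider assessment of folliculitis, atrophy, striae or infection |
| SAE reports (Section 17.2) | Serious events, with relationship to treatment | Non-serious reactions |
| Visit table (Section 10.2) | Weekly and final provider skin assessment | No row for adverse reactions |
| Section 14 | Efficacy endpoints and Skindex-16 | No by-arm summary of cream reactions |

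**Observation after the cream ends.** Inputs: RT lasts 5 weeks (Section 1.0); cream continues to 10-14 days after RT (Section 9.1); the last visit is 10-14 days after RT (Section 10.2).
- RT: 5 × 7 = 35 days.
- Scheduled end of cream: 35 + 10 = 45 to 35 + 14 = 49 days.
- Last visit: also 45 to 49 days.
- Longest gap: cream ends at 10 days, visit at 14 days: 14 − 10 = 4 days. If both fall on the same day, it is 0.

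**What full recording could show.** Inputs: 62 patients per arm (Section 14) and 1.6% for burning, pruritus and atrophy combined (Section 11).
- Expected MF reactions: 62 × 0.016 = 0.99.
- Chance of at least one: 1 − 0.984^62 = 0.632.
- One-sided 95% upper limit if none occurs: 1 − 0.05^(1/62) = 0.047.
- With all enrolled patients (143 / 2, about 71 per arm): 71 × 0.016 = 1.1 expected, a 68% chance of at least one, and an upper limit of 4.1%.
- At the interim (31 per arm): 31 × 0.016 = 0.50 expected, and an upper limit of 1 − 0.05^(1/31) = 0.092.

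**The case against.** Several parts of the other side's case are right, and they rule out stronger readings that a reader might infer.

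- **That Section 11 limits monitoring to erythema and desquamation.** It does not. The sentence describes expected radiation effects and contains no word of restriction.
- **That the trial cannot report MF harms.** The stopping rule has no severity threshold, so any recognised cream reaction should lead to a form entry. Skindex-16 compares subjective symptoms between randomised arms, and SAEs are reported. What is missing is structured, graded collection and a planned summary.
- **That Section 12.1 shows what the form omits.** That section concerns the primary objective. Other sections put the second-jar date, refill timing and interventions on the same form. The form is not shown, so a free-text field for reactions cannot be excluded. Free text would still not be systematic collection.
- **That there is no off-cream observation at all.** Patients who stop early are still assessed weekly and at the final visit. The gap concerns those who complete the cream, and reactions present at or starting after the last visit.
- **That follow-up is too short.** Section 3.2 says "Side effects are generally categorized as acute if occurring during or within 6 weeks of radiation treatment", but it also puts the peak at about 1-2 weeks after RT, which the visit matches. Healing is not an objective in Section 2.0. Length of follow-up is a debatable design choice.
- **That calling the procedures "felt to be of minimal risk" in Section 17.0 lowers the monitoring.** Section 16.2 assigns Phase III trials to the Data and Safety Monitoring Board, and no lost monitoring step can be shown.

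It can also be said that about one expected event supports no useful test, and that itch or burning cannot be attributed to cream rather than radiation in one patient. Both are true. They argue for a descriptive table, not for leaving the data uncollected.

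**Conclusion.** The point holds as a gap in collection and reporting. The local reactions listed in Section 11 have no described scheduled, graded assessment and no planned by-arm summary, so comparative harms data would be sparse and unsystematic. For patients who complete the cream, planned observation after it ends is about 0 and at most 4 days.

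The gain from closing the gap is real but modest: about 1 expected MF reaction in 62, or an upper limit of about 4.7% if none is seen.

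This rests on three assumptions:
- The form has no structured reaction fields beyond those the protocol text mentions.
- The 1.6% rate carries over to irradiated chest-wall skin. The protocol does not say in which patients it was observed.
- The 1.6% covers burning, pruritus and atrophy only. The protocol gives no rate for the other listed reactions.

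The planned rates imply 0.50 × 62 + 0.25 × 62 = 46.5 patients with a grade 2 or higher reaction at some time. This does not size the follow-up gap, because the number unresolved at the last visit is unknown.

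**What to change.** Add structured items to the existing Provider Skin Toxicity Assessment Form, completed at the weekly checks and the 10-14 day visit already scheduled. The items should cover the local reactions that Section 11 lists, for example folliculitis, infection, contact dermatitis, atrophy or striae, and pigment change. For each, record type, grade, onset, whether cream was stopped, and whether the reason was a cream reaction or moist desquamation.

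In Section 14, add one descriptive table of these items by arm, without a significance test. Supply it to the monitoring board with the interim analysis, and keep the by-arm version from the blinded study team.

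Optionally, for patients with an unresolved reaction at the last visit, record the outcome by phone or chart review up to 6 weeks after RT. This would add outcome data but is not needed for the stated objectives.

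The cost is slightly more form completion and one table. No new clinic visit, test or assessor is needed, and cream use and the primary analysis do not change.
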